6.1 DETERMINATION OF SAMPLE SIZE

The sample size for this study is based on the primary efficacy objective and primary biomarker objective.

Based on 150 patients, the maximum half width of the 2-sided 95% CI of the estimated ORR will be within 8%.

Additionally, based on 120 biomarker-evaluable patients (80% of the study population), with a minimum follow-up of 6 months during the primary analysis, and with 28 patients in the smaller biomarker positive or negative group (19% of the study population), the study primary biomarker analysis will have 89% and 79% power to detect PFS difference if the HRs of PFS between the biomarker positive vs. negative group is 0.50 or 0.55, respectively. The above-mentioned power is for a 2-sided test with a significance level of 0.1, assuming a median PFS of 4 months for the subgroup with a shorter median PFS.

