4. STATISTICAL METHODOLOGIES

4.1 Sample size:

The sample size for this study is based on the primary efficacy objective and primary biomarker objectives. Based on 150 patients, the maximum half width of the 2-sided 95% CI of the estimated ORR will be within 8%. Additionally, based on 150 patients, there will be at least 80% power to detect a statistical improvement in PFS for bTMB high group vs bTMB low subgroup. The power listed in the table below is based on the following assumptions: the test is 2-sided, significance level is 0.10, both biomarker subgroups have at least 25% of the patients (i.e., 37 or more patients in both groups), median PFS is 4 months for the subgroup with a shorter median PFS, the HR of PFS between the subgroup with a shorter PFS versus the other subgroup is 0.6 or lower, the recruitment duration is one year, the follow-up time from last patient in is 18 months, and the dropout rate is 5%.

n =150	Power		
	Biomarker ≥ 25th percentile vs.< 25th percentile	Biomarker ≥ 50th percentile vs. < 50th percentile	Biomarker ≥ 75th percentile vs. < 75th percentile
0.4	100%	100%	100%
0.5	97%	99%	97%
0.6	83%	92%	84%
0.7	58%	69%	58%

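### The protocol gives one power figure whichever biomarker group is smaller, but at 6 months' follow-up power depends on which group is small and on an unstated accrual period

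*Protocol*

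**What the plan says.** Protocol Section 6.1, repeated in the synopsis, bases the sample size partly on the primary biomarker objective. The calculation is "based on 120 biomarker-evaluable patients (80% of the study population"). Its timing is given as "with a minimum follow-up of 6 months during the primary analysis". The split is described as "with 28 patients in the smaller biomarker positive or negative group (19% of the study population"), so either group may be the small one. On that basis "the study primary biomarker analysis will have 89% and 79% power to detect PFS difference". The two powers belong to hazard ratios of 0.50 and 0.55 in that order, each taken as positive over negative. Testing is two-sided at the 0.10 level. One further input is listed: "assuming a median PFS of 4 months for the subgroup with a shorter median PFS". Section 6.1 gives no accrual period and no dropout rate.

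SAP Section 4.1 contains a separate power table for 150 patients, which assumes that "the recruitment duration is one year, the follow-up time from last patient in is 18 months, and the dropout rate is 5" per cent. That table has separate columns for splits at the 25th, 50th and 75th percentiles.

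**The concern.** The hazard ratio is defined as positive versus negative and is below 1, so the negative group always has the 4-month median and the positive group the longer one (8 months at HR 0.50, 7.3 at HR 0.55). At 6 months' minimum follow-up a noticeable share of the longer-PFS group has not yet had an event. Putting 92 patients in that group rather than 28 changes both the number of events and their split between groups. One pair of powers is therefore unlikely to describe both situations that the sentence covers.

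At stake is the accuracy of a design figure. Section 6 times the primary biomarker analysis at 6 months after the last enrolment, and Section 6.1 is the only power statement that uses that timing and allows for non-evaluable patients. A reader cannot check it without an accrual period.

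**Working it through.** **Inputs.** From Protocol 6.1: 120 patients split 28 and 92, two-sided alpha 0.10 (z = 1.645), negative-group median 4 months, HR 0.50 or 0.55, follow-up F = 6 months after the last patient. From SAP 4.1: accrual A = 12 months and 5% dropout, taken here as none or as 5% per year. Assumed: exponential PFS and uniform accrual.

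**Event probability.** For hazard λ without dropout, P = 1 − [exp(−λF) − exp(−λ(F+A))]/(λA).
- Negative group, λ = ln 2/4 = 0.1733: P = 0.851.
- Positive group, HR 0.50, λ = 0.0866: P = 0.630.
- Positive group, HR 0.55, λ = 0.0953: P = 0.664.

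**Schoenfeld power** = Φ(√(D·p(1−p))·|ln HR| − 1.645), with p = 28/120 and p(1−p) = 0.1789.

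At HR 0.50, no dropout:
- Positive group small: D = 28×0.630 + 92×0.851 = 96.0, power Φ(2.872 − 1.645) = 89.0%.
- Negative group small: D = 92×0.630 + 28×0.851 = 81.8, power Φ(2.652 − 1.645) = 84.3%.

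At HR 0.55, no dropout:
- Positive group small: D = 96.9, power 80.1%.
- Negative group small: D = 84.9, power 75.3%.

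With 5% annual dropout the positive-small case becomes 88.5% and 79.4%, which rounds to the printed pair. The negative-small case becomes 83.7% and 74.6%.

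**Check on the formula.** With 12 months' accrual, 18 months' follow-up and no dropout, it reproduces the SAP 4.1 table: at HR 0.6, 83.0/91.9/84.2 against a printed 83/92/84; at HR 0.7, 57.6/69.0/58.4 against 58/69/58. Freedman's formula with unequal allocation does not give 89% and 79% in either direction at 12 months (75.8%/67.3% and 92.7%/84.9%).

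**The log-rank test itself.** Simulation used 40,000 runs per cell, with a standard error of about 0.2 points. Pairs are HR 0.50 / HR 0.55, in per cent.

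| Accrual, dropout | Schoenfeld, positive small | Schoenfeld, negative small | Simulation, positive small | Simulation, negative small |
|---|---|---|---|---|
| 12 months, none | 89.0 / 80.1 | 84.3 / 75.3 | 85.4 / 76.1 | 88.2 / 79.5 |
| 12 months, 5% a year | 88.5 / 79.4 | 83.7 / 74.6 | 84.9 / 75.3 | 87.9 / 79.0 |
| 18 months, none | 90.5 / 82.0 | 87.0 / 78.3 | 87.1 / 78.4 | 90.1 / 82.1 |
| 18 months, 5% a year | 90.0 / 81.3 | 86.3 / 77.5 | 86.7 / 77.5 | 89.5 / 80.9 |
| 24 months, none | 91.4 / 83.1 | 88.6 / 80.2 | 88.8 / 79.9 | 91.1 / 83.2 |
| 24 months, 5% a year | 90.8 / 82.4 | 87.9 / 79.3 | 87.8 / 78.9 | 90.4 / 82.0 |

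A separate 15,000-run simulation at 18 months without dropout gave 87.5% and 78.5% in the weaker direction. Reading the 5% as a flat loss of events, instead of an annual rate, lowers the 12-month Schoenfeld figures by about one further point (82.6% and 73.4% in the weaker direction).

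**Why the methods disagree on direction.** Schoenfeld fixes the information per event at p(1−p), so only the total D matters. Information from events per group, 1/(1/d₁ + 1/d₂), depends on how many events the small group supplies. At HR 0.50, 12 months and no dropout:
- Positive small: 17.6 and 78.3 events, information 14.4, power 83.8%.
- Negative small: 58.0 and 23.8 events, information 16.9, power 88.6%.

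This agrees with the simulation in direction. Either way one direction is near the printed pair and the other is 3 to 5 points lower.

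**The case against.** The strongest reply is that Section 6.1 gives no accrual period, and the one year and 5% come from a different SAP calculation (150 patients, at least 25% in each group, 18 months' follow-up). Nothing says the two share assumptions, and the SAP table is reproduced best with no dropout, where the 12-month pair is 89% and 80%, not 89% and 79%. Protocol Section 3.2 expects about 3 years in total; less 18 months' follow-up, that implies about 18 months of accrual, and the shortfall is then only about 0.5 to 3 points. This stands, and it limits what can be claimed.

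A reader might infer that the printed power holds in only one direction whatever the accrual. The documents do not support that: at about 24 months both directions essentially meet 89% and 79%. A reader might also infer that high cutoffs such as bTMB ≥ 16, if they make the positive group small, are the established weak case. Simulation points that way, but Schoenfeld, which reproduces the SAP table, points the other way.

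It can also be said that the SAP's separate percentile columns already show power by direction. They do so for all 150 patients and 18 months' follow-up, where the two directions differ by about one point (83% and 84% at HR 0.6). They do not cover 120 evaluable patients at 6 months, where the gap is larger. Lastly, the protocol calls the study hypothesis-generating and no decision turns on this figure. That is fair, and it is why the point is minor.

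**Conclusion.** The point holds in a limited form. A single power is stated for two situations that differ by about 3 to 5 points at one-year accrual. On the SAP's recruitment assumption (5% dropout read as annual, or none), the weaker direction has about 84–85% at HR 0.50 and 75% at HR 0.55, so the chance of missing an HR of 0.55 is about 25%, not 21%. At 18 months' accrual the weaker direction is about 86–88% and 77–79%. At about 24 months the gap from the stated figures essentially closes, but neither document supports that accrual.

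These figures rest on exponential PFS, uniform accrual and an accrual period that the protocol does not state. That one direction is weaker does not depend on the method; which one does. The result does not show that the study is too small or that the printed pair was miscalculated: 89% and 79% is a sound Schoenfeld result for one of the two cases. Severity is minor.

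**What to change.** In Protocol Section 6.1 and the synopsis, state the accrual period and the dropout assumed, including whether dropout is annual, and name the power method. Then either give power for each direction under those assumptions or quote the lower figure. At one-year accrual the lower figure is about 84% for HR 0.50 and 75% for HR 0.55; if another accrual was intended, recompute with that value.

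The cost is a few words in two places and a slightly less favourable stated power. Sample size, cutoffs, test and analysis timing stay as they are.

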6.2 SUMMARIES OF CONDUCT OF STUDY

The number of patients who enroll in, discontinue, or complete the study will be summarized. Reasons for premature study withdrawal will be listed and summarized. Enrollment and major protocol deviations will be listed and evaluated for their potential effects on the interpretation of study results.

6.3 SUMMARIES OF DEMOGRAPHIC AND BASELINE CHARACTERISTICS

Demographic and baseline characteristics (e.g., age, sex) will be summarized by using means, SDs, medians, and ranges for continuous variables, and proportions for categorical variables, as appropriate.

6.4 EFFICACY ANALYSES

The efficacy analysis population will be based on all patients who have received at least one dose of study drug.

6.4.1 Primary Efficacy Endpoint

The primary efficacy endpoint of this study is investigator-assessed ORR, defined as the proportion of patients whose confirmed best overall response is either a PR or CR per RECIST v1.1. For this analysis, patients not meeting these criteria, including patients without at least one post-baseline response assessment, will be considered non-responders. An estimate of the ORR from all patients who received study drug and the 95% CI will be calculated by using the Blaker method.

6.4.2 Secondary Efficacy Endpoints

Secondary efficacy endpoints include OS and investigator (INV)-assessed duration of response (DOR) and PFS per RECIST v1.1.

DOR will be analyzed for the subset of patients who achieved an objective response. DOR is defined as the time from the initial occurrence of documented CR or PR until documented disease progression as determined by the investigator, or death, whichever occurs first. Median and range will be presented for a descriptive summary.

PFS is defined as the time from the first dose of study drug to the time of disease progression or death from any cause during the study, whichever occurs first. Patients who have not experienced disease progression or death at the time of analysis will be censored at the time of the last tumor assessment. Patients with no post-baseline tumor assessment will be censored at the time of first dose.

OS is defined as the time from the first dose of study drug to the time of death from any cause during the study. Patients who are still alive at the time of analysis will be censored at the time of their last study assessment (for active patients) or at the last date known alive (for patients in follow-up).

PFS and OS of patients in this study will be summarized graphically and with descriptive statistics such as median and landmark PFS by using the Kaplan-Meier (K-M) methodology. The Brookmeyer-Crowley methodology will be used to construct the 95% CI for the median PFS and OS (Brookmeyer and Crowley 1982). K-M methods will also be used to estimate landmark PFS, along with the corresponding 95% CI, by using Greenwood's formula.

6.4.3 Exploratory Efficacy Endpoints

The relationship between efficacy, baseline characteristics, and biomarkers may also be explored.

6.5 SAFETY ANALYSES

Safety will be assessed through summaries of adverse events, including protocol-defined events of special interest, changes in laboratory test results, changes in vital signs, and exposure to study.

Verbatim descriptions of adverse events will be mapped to thesaurus terms using MedDRA. Adverse event data will be listed by study site, patient number, and study day. Events occurring on the day of or after administration of the first dose of treatment will be summarized by thesaurus term, appropriate thesaurus levels, and NCI CTCAE v4.0 grade. Serious adverse events, including deaths, will be listed separately and will be summarized. For events of varying severity, the highest grade will be used in summaries.

Relevant laboratory tests and vital sign (heart rate, respiratory rate, blood pressures, and temperature) data will be displayed by time, with Grade 3 and 4 values identified, where appropriate. Additionally, all laboratory data will be summarized by NCI CTCAE v4.0 grade.

6.6 BIOMARKER ANALYSES

Biomarker analysis population will be based on all patients who have received at least one dose of study drug and have baseline biomarker assessment.

6.6.1 Primary Biomarker Analyses

K-M curves and a log-rank test will be used to evaluate the differences in INV-assessed PFS between mutation positive versus negative groups at various cutoff points. Tests will be two-sided at a significance level of 0.10.

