Systemic corticosteroids and TNF- α inhibitors may attenuate potential beneficial immunologic effects of treatment with atezolizumab. Therefore, in situations where systemic corticosteroids or TNF- α inhibitors would be routinely administered, alternatives, including antihistamines, should be considered first by the treating physician. If the alternatives are not feasible, systemic corticosteroids and TNF- α inhibitors may be administered at the discretion of the treating physician except in the case of patients for whom CT scans with contrast are contraindicated (i.e., patients with contrast allergy or impaired renal clearance).

Systemic corticosteroids are recommended, with caution at the discretion of the treating physician, for the treatment of specific adverse events when associated with atezolizumab therapy.

Statistical Methods

Primary Efficacy Analyses

The efficacy analysis population will be based on all patients who have received at least one dose of study drug. The primary efficacy endpoint of this study is investigator-assessed objective response rate (ORR), defined as the proportion of patients whose confirmed best overall response is either a partial response (PR) or complete response (CR) per RECIST v1.1. For this analysis, patients not meeting these criteria, including patients without at least one post-baseline response assessment, will be considered non-responders. An estimate of the ORR from all patients who received study drug and the 95% confidence interval (CI) will be calculated by using the Blaker method.

Primary Biomarker Analyses

Biomarker analysis population will be based on all patients who have received at least one dose of study drug and have baseline biomarker assessment. Kaplan-Meier (K-M) curves and a log-rank test will be used to evaluate the differences in investigator-assessed PFS between mutation positive versus negative groups at various cutoff points. Tests will be two-sided at a significance level of 0.10.

Determination of Sample Size

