2. OBJECTIVES AND ENDPOINTS

The aim of this study is to evaluate the clinical efficacy of atezolizumab as a single-agent, first-line therapy in patients with immunotherapy-naïve, Stage IIIB–IVB NSCLC. Diagnostic selection of patients will not be a criterion for enrollment.

The primary biomarker objective is to measure tumor mutational burden from blood (bTMB) and to evaluate whether it can predict for improved clinical outcomes with atezolizumab. Clinical outcome, as measured by PFS, will be correlated to bTMB retrospectively to define the threshold for positivity. Specific objectives and corresponding endpoints for the study are outlined in [Table 3](#).

Table 3 Objectives and Corresponding Endpoints

Objectives	Corresponding Endpoints
Primary Efficacy Objective:	

 To evaluate the clinical efficacy of atezolizumab 	
 INV-assessed ORR by RECIST v1.1
Secondary Efficacy Objective:	

 To evaluate the efficacy of atezolizumab 	
 INV-assessed ORR by RECIST v1.1 INV-assessed PFS by RECIST v1.1 INV-assessed duration of response by RECIST v1.1 Overall survival
Safety Objective:	

 To evaluate the safety and tolerability of atezolizumab 	
 Incidence of adverse events, with severity determined through use of NCI CTCAE v4.0
Primary Biomarker Objective:	

 To evaluate whether “positive vs. negative bTMB” defined at various bTMB quantiles can predict for improved PFS with atezolizumab 	
 Relationship between INV-assessed PFS and various bTMB quantiles
Secondary Biomarker Objectives	

 To evaluate the correlation between clinical outcomes including but not limited to PFS, PFS rate at 6, 9, and 12 months, ORR, and various definitions of positive bTMB 	
 Relationship between efficacy endpoints including INV-assessed PFS rate at 6, 9, and 12 months, ORR and various bTMB quantiles and efficacy
Exploratory Biomarker Objectives in Blood:	

 To evaluate whether higher expression of an immune-related gene signature in blood PBMCs predicts for improved PFS with atezolizumab 	
 Relationship between PFS and expression of an immune gene signature in PBMCs

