6. STATISTICAL CONSIDERATIONS AND ANALYSIS PLAN

There will be approximately 150 patients enrolled in the study. Safety analyses will include all patients who receive at least one dose of study drug. Biomarker analyses will include all patients who received at least one dose of study drug and have baseline biomarker assessment. The primary efficacy analysis measured by ORR and the primary biomarker analysis will be performed after all patients complete 6 months of follow-up (i.e., 6 months after the final patient has been enrolled). The final analysis will be performed at the end of the study, 18 months after all patients have been enrolled. *The overall survival analysis will be updated once the long-term follow-up data is available, and will be summarized in a separate report. Safety reporting for patients who remain on study drug will also be included.*

In addition, OS data collected through the external death registry data after study completion during the optional long-term follow-up will be updated periodically (e.g., every 1–2 years) based on data availability.

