3.1 Protocol Synopsis

The protocol synopsis (see protocol).

3.2 Objectives and Endpoints:

The objectives and corresponding endpoints for the study are outlined in table below.

Objectives	Corresponding Endpoints
Primary Efficacy Objective:	
To evaluate the clinical efficacy of Atezolizumab	ORR according to RECIST v1.1 as assessed by the investigator
Secondary Efficacy Objective:	
To evaluate the efficacy of Atezolizumab	Investigator-assessed PFS according to RECIST v1.1
	Investigator-assessed disease control rate and duration of response according to RECIST v1.1
	Overall survival
Safety Objective:	
To evaluate the safety and tolerability of atezolizumab	Incidence of adverse events, with severity determined through use of NCI CTCAE v4.0
Primary Biomarker Objectives:	
To evaluate whether "positive" bTMB (defined as bTMB ≥ 16 , and bTMB ≥ 10) is associated with improved PFS with the treatment of atezolizumab	Relationship between PFS and bTMB (≥ 16 vs < 16) and between PFS and bTMB (≥ 10 vs < 10)
Secondary Biomarker Objective:	
To evaluate whether "positive bTMB" defined at various bTMB cutoff points or quantiles can predict for improved PFS with atezolizumab.	Relationship between PFS and various bTMB cutoff points, defined as range 4 to 24 by twos, and quantiles, except the primary cutoff points 16 and 10
To evaluate the correlation between clinical outcomes including but not limited to PFS rate at 6, 9, and 12 months, ORR, disease control rate and various definitions of positive bTMB.	Relationship between efficacy endpoints including PFS rate at 6, 9, and 12 months, disease control rate, ORR and various bTMB cutoff points and quantiles

Exploratory Biomarker Objectives in Blood:	
To evaluate whether higher expression of an immune-related gene signature in blood PBMCs predicts for improved PFS with atezolizumab	Relationship between PFS and expression of an immune gene signature in PBMCs
To assess whether bTMB is altered as a result of treatment with immunotherapy	Relationship between bTMB and treatment with immunotherapy
To assess the status of additional circulating biomarkers related to immunotherapy and NSCLC and outcomes with atezolizumab	Relationship between circulating biomarkers related to immunotherapy and NSCLC and efficacy
Exploratory Biomarker Objectives in Tissue:	

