3.3 Timing of Analyses

The primary efficacy analysis measured by ORR may be performed after all patients complete 6 months of follow-up (i.e. 6 months after last patient enrolled into the study). If the primary efficacy analysis is not performed at 6 months of follow-up, it will be performed during the final analysis. The final analysis will be performed at the end of the study, 18 months after all patients have been enrolled.

One interim analysis is planned 6 months after one-half of the patients have been enrolled. The purpose of the interim analysis is to provide preliminary results in evaluating the biomarker cutoff and to perform a futility analysis. The futility criteria to stop the study will be met if the true ORR is more likely $\leq 5\%$ rather than $\geq 15\%$, or if 4 or fewer patients have an objective response from the first 75 enrolled and treated patients. The chance of stopping the study is $> 67\%$ if the true ORR is 5% or less. The chance of stopping the study is $< 1\%$ if the true ORR is 15% or larger. No type-1 error adjustments will be made for the interim analysis.

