4.7.1 Primary Biomarker Analyses

K-M curves and a log-rank test will be used to evaluate the differences in PFS between bTMB high versus low groups at 16 and 10 two different cutoff points (i.e. bTMB ≥ 16 vs < 16 , and bTMB ≥ 10 vs < 10). The Gatekeeping testing procedures will be used to test PFS differences at these two primary bTMB cut off points. PFS difference at cutoff point 16 will be tested first. If there is statistical significance in PFS difference bTMB ≥ 16 vs < 16 groups, we will claim statistical significant difference in PFS between bTMB ≥ 16 vs < 16 groups, and we will further test PFS difference at cutoff 10. We can only claim PFS difference between bTMB ≥ 10 vs < 10 groups if both tests for cutoff point 16 and cut off point 10 are statistically significant.

The statistical tests for primary analysis as well as for other analyses comparing efficacy differences between bTMB high group vs low group will be two-sided at a significance level of 0.10. The corresponding bTMB group differences will be estimated and two-sided 90% confidence interval will be provided. All other statistical tests used in the study will be two-sided at level of 0.05. Their corresponding point estimators will be estimated and two-sided 95% confidence interval will be provided.

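### Protocol and SAP define different primary biomarker analyses (cutoffs, error control, timing, evaluable number), and nothing in the available text says which governs

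*Protocol*

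**What the plan says.** **Hypothesis.** Protocol Table 3 gives the primary biomarker endpoint as "Relationship between INV-assessed PFS and various bTMB quantiles". Protocol Section 2 adds that PFS "will be correlated to bTMB retrospectively to define the threshold for positivity". The synopsis and Section 6.6.1 then compare PFS "between mutation positive versus negative groups at various cutoff points. Tests will be two-sided at a significance level of 0.10". No cutoffs are listed and no order or adjustment is stated.

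SAP 3.2 and 4.7.1 name two primary cutoffs, 16 and then 10: "The Gatekeeping testing procedures will be used to test PFS differences at these two primary bTMB cut off points". A claim at 10 requires significance at both. The Protocol's primary objective, positivity "defined at various bTMB cutoff points or quantiles can predict for improved PFS with atezolizumab", is a secondary objective in SAP 3.2.

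**Timing.** Protocol Section 6: "the primary biomarker analysis will be performed after all patients complete 6 months of follow-up". SAP 3.3 says "The primary efficacy analysis measured by ORR may be performed after all patients complete 6 months of follow-up" and also dates the interim and the 18-month final analysis. It gives no time for the primary biomarker test.

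**Numbers.** Protocol 6.1 uses 120 evaluable patients (80% of 150) with 28 in the smaller group, and states 89% and 79% power at HR 0.50 and 0.55. SAP 4.1 uses all 150, at least 25% (37 or more) per group, one year of recruitment, 18 months of follow-up and 5% dropout. It states at least 80% power at HR 0.6 or lower. SAP 4.2 nevertheless limits the biomarker population to evaluable baseline samples, and SAP 4.7 ties evaluability to MSAF of at least 1%.

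**The concern.** The bTMB objective is one of the two that set the sample size, and SAP 4.7.1 intends to claim significance on it. A reader holding both documents cannot tell which cutoffs carry that claim, when they are tested, or on how many patients.

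Part of the difference is the ordinary narrowing that a SAP does. But a Protocol primary objective has also become secondary, and error control, power base and follow-up have all changed without acknowledgement. SAP 2 says only that the document specifies the study's analyses. The reason for choosing 16 and 10 also matters: both documents plan an interim look that helps evaluate the biomarker cutoff, so the plan should record where these two values came from.

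**Working it through.** **Method.** PFS is exponential with a 4-month median in the shorter-PFS group (both documents), so λ = ln 2/4 = 0.1733 per month, and HR·λ in the other group. Accrual is uniform over A = 12 months (SAP 4.1; assumed for the Protocol, which gives none with its power figure). With minimum follow-up F:

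- P(event) = 1 − [e^(−λF) − e^(−λ(F+A))]/(λA)
- D = expected events summed over both groups; p = share in the smaller group
- Power = Φ(|ln HR|·√(D·p(1−p)) − 1.645), two-sided 0.10

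HR is taken as longer-PFS over shorter-PFS group. At F = 18, P(event) is 0.981 in the shorter-PFS group and 0.912 in the other at HR 0.60. At F = 6 these are 0.851 and 0.694.

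**Protocol figure.** 120 patients, 28 in the smaller (longer-PFS) group, F = 6: D = 96.0 and 96.9, giving 89.0% and 80.1% against the stated 89% and 79%. With 9 months' accrual it is 87.8% and 78.6%. The figure reproduces. The smaller group is 28/120 = 23.3% of evaluable patients, or 28/150 = 18.7% of all.

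**SAP figure.** 150 patients, 37 in the smaller (longer-PFS) group, HR 0.60, F = 18: D = 37×0.912 + 113×0.981 = 144.6; p(1−p) = 0.1858; 0.5108×√26.87 − 1.645 = 1.003; power 84.2%. With the smaller group having the shorter PFS it is 83.0%. The SAP states 84% and 83%.

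**SAP scenario on the Protocol's 120 evaluable.** A 25/75 split is now 30 patients: D = 115.7; p(1−p) = 0.1875; 0.5108×√21.69 − 1.645 = 0.734; power 76.9%. Ranges below cover either group being the smaller one.

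| N / smaller group | Follow-up | HR | No dropout | 5% off N |
|---|---|---|---|---|
| 150 / 37 | 18 mo | 0.60 | 83.0–84.2% | 81.3–82.5% |
| 150 / 75 | 18 mo | 0.60 | 91.9% | 90.7% |
| 120 / 30 | 18 mo | 0.60 | 75.5–76.9% | 73.6–75.0% |
| 120 / 37 | 18 mo | 0.60 | 80.3–81.2% | 78.5–79.5% |
| 120 / 40 | 18 mo | 0.60 | 81.8–82.6% | 80.0–80.8% |
| 120 / 30 | 18 mo | 0.55 | 85.7–87.1% | 84.1–85.6% |
| 120 / 30 | 18 mo | 0.50 | 92.9–94.1% | 91.8–93.1% |
| 120 / 30 | 6 mo | 0.60 | 66.6–70.5% | 64.7–68.6% |

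A log-rank simulation of 120/30 at 18 months and HR 0.60 gave 73% to 78%.

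**Error rate.** Under the SAP's fixed order, the chance of any false primary claim is at most 10%. If instead every Protocol cutoff were tested at 0.10 and any significant one counted, the correlation between the statistics at quantiles p < q is √[p(1−q)/(q(1−p))]. Two tertile cutoffs then give about 17–18% and three quartile cutoffs 23–25% (multivariate-normal draws and log-rank simulation together). The number of cutoffs is assumed, because the Protocol gives none.

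**The case against.** The strongest reply is that the SAP governs by its nature, that 16 and 10 lie within the Protocol's open set of cutoffs, and that fixing and ordering them is stricter. The Protocol also calls the study hypothesis-generating, so searching for a threshold is legitimate. Much of this stands. It removes any reading that the trial's primary biomarker error rate is 17–25%. Those figures arise only if the Protocol text were followed, with an assumed number of cutoffs and any significant one counted.

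The power criticism also has limits. SAP 4.1 states a count of 37 as well as a share, and 120/37 still gives about 79–81%. A reader might infer that the biomarker objective is underpowered in general, but at the Protocol's own effect sizes and 18 months, 120/30 gives 84–87% (HR 0.55) and 92–94% (HR 0.50).

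A reader might also infer that the MSAF condition removes patients beyond the Protocol's 20% non-evaluable share. Nothing shows this; it may simply be how the assay defines that share. Nor do the documents show that 16 and 10 came from this trial's PFS data, or that the SAP sets the test at 18 months, which is only a power assumption.

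The SAP still describes survival data from public sources, which the Protocol's amendment summary says was removed from Section 3.1. It may therefore have been written against an earlier Protocol. That might explain some of the differences, but it does not say which text applies.

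**Conclusion.** The inconsistency is real and should be fixed. It lies between the documents; neither power calculation is wrong on its own inputs. The SAP's minimum of 80% at HR 0.60 with a 25/75 split does not hold on the 120 evaluable patients that the Protocol expects: power is 74–77% at 18 months and 64.7–70.5% at the Protocol's 6 months. With 120 evaluable, 80% at HR 0.60 and 18 months needs roughly a third of patients in the smaller group. The shortfall at 18 months is confined to hazard ratios near 0.60.

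This rests on exponential PFS, 12-month accrual, and the Protocol's 80% evaluable share. The shares at or above 16 and 10 are not given. Front matter is missing from the copies read, so the absence of a governing statement is limited to the available text.

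**What to change.** In the SAP now:

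- Add a note on changes from the Protocol, saying that 4.7.1 governs and why 16 and 10 were chosen.
- In 3.3, name one data cut for the primary biomarker test.
- In 4.1, restate power on the expected evaluable number (for example 120) and the expected share at or above 16 and 10.

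At the next Protocol amendment, align the synopsis, Table 3 and 6.6.1 with SAP 4.7.1. Place the other cutoffs, the quantiles and the threshold search in the secondary tier that the SAP already uses. A new exploratory label would create a fresh mismatch.

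The SAP edits are text only. The Protocol change needs IRB/EC approval under Section 9.6 and can wait for an amendment made for other reasons. The price is a less favourable stated power: 74–77% in place of 83–84% at HR 0.60 and a 25/75 split. On the data cut, 6 months costs about 6 to 9 points against 18 months (120/30, HR 0.60), while 18 months delivers the result a year later.
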